8.5.3 Reporting procedures to FDA

In this trial, serious, unexpected adverse events believed to be definitely, probably or possibly related to the study treatment will be reported to the Food and Drug Administration via the MedWatch 3500A Form. The Michigan IND/IDE Assistance Program (MIAP) (University of Michigan) will assist the IND Sponsor in reporting SAEs to the FDA that meet the reporting requirements in 21 CFR 312.32. This reporting could include the initial report and follow-up reports when appropriate for the event.

8.6 Routine Reporting

All other adverse events- such as those that are expected, or are unlikely or definitely not related to the study participation- are to be reported annually as part of regular data submission.

8.7 Reporting of Unanticipated Problems

There are types of incidents, experiences and outcomes that occur during the conduct of human subjects research that represent unanticipated problems but are not considered adverse events. For example, some unanticipated problems involve social or economic harm instead of the physical or psychological harm associated with adverse events. In other cases, unanticipated problems place subjects or others at increased risk of harm, but no harm occurs.

Upon becoming aware of any incident, experience, or outcome (not related to an adverse event) that may represent an unanticipated problem, the investigator should assess whether the incident, experience, or outcome represents an unanticipated problem. The incident, experience or outcomes is considered unanticipated if it meets all of the following criteria:

1. Unexpected (in terms of nature, severity, or frequency);
2. Related or possibly related to participation in the research; and
3. Suggests that the research places subjects or others at a greater risk of harm than was previously known or recognized.

If the investigator determines that the incident, experience, or outcome represents an unanticipated problem, the investigator must report it to the IRB within 7 calendar days of the study team becoming aware of the problem.

8.8 Safety Report Reconciliation

The Sponsor will reconcile the clinical database SAE reports transmitted to BMS Global Pharmacovigilance ([contact]). Frequency of reconciliation should be every 3 months and prior to the database lock or final data summary. BMS GPV&E

will email, upon request from the Investigator, the GPV&E reconciliation report. Requests for reconciliation should be sent to [contact]. The data elements listed on the GPV&E reconciliation report will be used for identification purposes. If the Investigator determines a report was not transmitted to BMS GPV&E, the report should be sent immediately to BMS.

9.0 DRUG INFORMATION

9.1 Nivolumab

- Other names for the drug: Opdivo
- Description: Injection: 100 mg/10 mL solution in a single-dose vial.
- Classification - type of agent: Immunomodulatory; checkpoint inhibitor
- Mode of action:
Binding of the PD-1 ligands, PD-L1 and PD-L2, to the PD-1 receptor found on T cells, inhibits T-cell proliferation and cytokine production. Upregulation of PD-1 ligands occurs in some tumors and signaling through this pathway can contribute to inhibition of active T-cell immune surveillance of tumors. Nivolumab is a human immunoglobulin G4 (IgG4) monoclonal antibody that binds to the PD-1 receptor and blocks its interaction with PD-L1 and PD-L2, releasing PD-1 pathway-mediated inhibition of the immune response, including the anti-tumor immune response. In syngeneic mouse tumor models, blocking PD-1 activity resulted in decreased tumor growth.
Combined nivolumab (anti-PD-1) and ipilimumab (anti-CTLA-4) mediated inhibition results in enhanced T-cell function that is greater than the effects of either antibody alone, and results in improved anti-tumor responses in metastatic melanoma. In murine syngeneic tumor models, dual blockade of PD-1 and CTLA-4 resulted in increased anti-tumor activity.
- Pharmacokinetics:
Nivolumab pharmacokinetics (PK) were assessed using a population PK approach for both single-agent nivolumab and nivolumab with ipilimumab.
nivolumab as a single agent: The PK of single-agent was studied in patients over a dose range of 0.1 to 20 mg/kg administered as a single dose or as multiple doses of nivolumab every 2 or 3 weeks. Nivolumab clearance decreases over time, with a mean maximal reduction (% coefficient of variation [CV%]) from baseline values of approximately 24.5% (47.6%) resulting in a geometric mean steady state clearance (CLss) (CV%) of 8.2 mL/h (53.9%); the decrease in CLss is not considered clinically relevant. The geometric mean volume of distribution at steady state (Vss) (CV%) is 6.8 L (27.3%), and geometric mean elimination half-life (t_{1/2}) is 25 days (77.5%). Steady-state concentrations of nivolumab were reached by approximately 12 weeks when administered at 3 mg/kg every 2 weeks, and systemic accumulation was approximately 3.7-fold. The exposure to nivolumab increased dose proportionally over the dose range of 0.1 to 10 mg/kg administered every 2 weeks.
Nivolumab with ipilimumab: The geometric mean (CV%) CL, Vss, and terminal halflife of nivolumab were 10.0 mL/h (50.3%), 7.92 L (30.1%), and 24.8 days (94.3%), respectively. When administered in combination, the CL of nivolumab was increased by 24%, whereas there was no effect on the clearance of ipilimumab.
- Side effects:
Nivolumab as a single agent: fatigue, rash, musculoskeletal pain, pruritus, diarrhea,

nausea, asthenia, cough, dyspnea, constipation, decreased appetite, back pain, arthralgia, upper respiratory tract infection, and pyrexia.

Nivolumab with ipilimumab: fatigue, rash, diarrhea, nausea, pyrexia, vomiting, and dyspnea.

- **Drug Interactions:**
No formal pharmacokinetic drug-drug interaction studies have been conducted with nivolumab.
- **Storage and stability:**
The product does not contain a preservative. After preparation, store the nivolumab infusion either:
 - at room temperature for no more than 8 hours from the time of preparation. This includes room temperature storage of the infusion in the IV container and time for administration of the infusion or
 - under refrigeration at 2°C to 8°C (36°F to 46°F) for no more than 24 hours from the time of infusion preparation. Do not freeze.
- **Preparation and Dispensing:**
Visually inspect drug product solution for particulate matter and discoloration prior to administration. Nivolumab is a clear to opalescent, colorless to pale-yellow solution. Discard the vial if the solution is cloudy, discolored, or contains extraneous particulate matter other than a few translucent-to-white, proteinaceous particles. Do not shake the vial.
 - Withdraw the required volume of nivolumab and transfer into an intravenous container.
 - Dilute nivolumab with either 0.9% Sodium Chloride Injection, USP or 5% Dextrose Injection, USP to prepare an infusion with a final concentration ranging from 1 mg/mL to 10 mg/mL.
 - Mix diluted solution by gentle inversion. Do not shake.
 - Discard partially used vials or empty vials of nivolumab.
- **Administration:**
Administer the infusion over 30 minutes through an intravenous line containing a sterile, non-pyrogenic, low protein binding in-line filter (pore size of 0.2 micrometer to 1.2 micrometer). Do not coadminister other drugs through the same intravenous line. Flush the intravenous line at end of infusion.
When administered in combination with ipilimumab, infuse nivolumab first followed by ipilimumab on the same day. Use separate infusion bags and filters for each infusion.
- **Availability:** Provided by Bristol Myers Squibb, Inc.
- **Return and Retention of Study Drug:**
- Handling and disposal of nivolumab should be per institutional guidelines for the handling and disposal of biologic and cytotoxic agents
- **Drug Accountability:**
- The investigator, or a responsible party designated by the investigator, must maintain a careful record of the inventory and disposition of nivolumab. The drug accountability records will capture drug receipt, drug dispensing, drug return and final disposition.

9.2 Ipilimumab

- Other names for the drug: Yervoy

- Description:

Injection: 200 mg/40 mL (5 mg/mL) (3)
- Classification - type of agent: Immunomodulatory; checkpoint inhibitor
- Mode of action: human cytotoxic T-lymphocyte antigen 4 (CTLA-4)-blocking antibody
- Pharmacokinetics:

The pharmacokinetics (PK) of ipilimumab was studied in 785 patients with unresectable or metastatic melanoma who received doses of 0.3, 3, or 10 mg/kg once every 3 weeks for 4 doses. The PK of ipilimumab is linear in the dose range of 0.3 to 10 mg/kg. Following administration of ipilimumab every 3 weeks, the systemic accumulation was 1.5-fold or less. Steady-state concentrations of ipilimumab were reached by the third dose; the mean C_{min} at steady state was 19.4 mcg/mL at 3 mg/kg and 58.1 mcg/mL at 10 mg/kg every 3 weeks. The mean value (percent coefficient of variation) based on population PK analysis for the terminal half-life ($t_{1/2}$) was 15.4 days (34%) and for clearance (CL) was 16.8 mL/h (38%). Specific Populations The effects of various covariates on the PK of ipilimumab were assessed in population PK analyses. The CL of ipilimumab increased with increasing body weight supporting the recommended body weight (mg/kg) based dosing. The following factors had no clinically important effect on the CL of ipilimumab: age (range: 23 to 88 years), sex, performance status, renal impairment, mild hepatic impairment, previous cancer therapy, and baseline lactate dehydrogenase (LDH) levels. The effect of race was not examined due to limited data available in non-Caucasian ethnic groups.

Renal Impairment: No clinically important differences in the CL of ipilimumab were found between patients with renal impairment and patients with normal renal function.

Hepatic Impairment: The effect of hepatic impairment on the CL of ipilimumab was evaluated in patients with mild hepatic impairment (n=76) compared to patients with normal hepatic function (n=708) in the population PK analyses, and no clinically important differences in the CL of ipilimumab were found. Ipilimumab has not been studied in patients with moderate or severe hepatic impairment.

- Side effects: Ipilimumab can result in severe and fatal immune-mediated reactions.
- Drug Interactions: No formal pharmacokinetic drug interaction studies have been conducted with ipilimumab.
- Storage and stability:
 - Store the diluted solution for no more than 24 hours under refrigeration (2°C to 8°C, 36°F to 46°F) or at room temperature (20°C to 25°C, 68°F to 77°F).
- Preparation and Dispensing:
 - Do not shake product.
 - Inspect parenteral drug products visually for particulate matter and discoloration prior to administration. Discard vial if solution is cloudy, there is pronounced discoloration (solution may have pale-yellow color), or there is foreign particulate matter other than translucent-to-white, amorphous particles.
 - Allow the vials to stand at room temperature for approximately 5 minutes prior to preparation of infusion.
 - Withdraw the required volume of ipilimumab and transfer into an intravenous bag.
 - Dilute with 0.9% Sodium Chloride Injection, USP or 5% Dextrose Injection, USP to

- prepare a diluted solution with a final concentration ranging from 1 mg/mL to 2 mg/mL. Mix diluted solution by gentle inversion.
 - Discard partially used vials or empty vials of ipilimumab.
- Administration:
 - Do not mix ipilimumab with, or administer as an infusion with, other medicinal products.
 - Flush the intravenous line with 0.9% Sodium Chloride Injection, USP or 5% Dextrose Injection, USP after each dose.
 - Administer diluted solution over 90 minutes through an intravenous line containing a sterile, non-pyrogenic, low-protein-binding in-line filter.
- Availability: Provided by Bristol Myers Squibb, Inc.
- Return and Retention of Study Drug: Handling and disposal of ipilimumab should be per institutional guidelines for the handling and disposal of biologic and cytotoxic agents
- Drug Accountability: The investigator, or a responsible party designated by the investigator, must maintain a careful record of the inventory and disposition of ipilimumab. The drug accountability records will capture drug receipt, drug dispensing, drug return and final disposition.

10.0 CORRELATIVES/SPECIAL STUDIES

Specimens will be collected for banking and archival purposes. Submission of samples for correlative studies is expected of all subjects at baseline and optional tumor biopsy will be performed for those who consent to it.

10.1 Sample Collection Guidelines

Prior to study enrollment, patients must have documented CDK12 loss on a prior biopsy (or cell-free DNA or other is allowed) of primary or metastatic tissue. Metastatic tissue is strongly preferred.

Willingness to provide archival tissue submission is mandatory. If archival tissue, contains inadequate tissue for NGS (i.e., less than 30% tumor content) or patient does not consent to fresh tissue biopsy, or fresh biopsy is not feasible, then patient may enroll in study if all other eligibility criteria are met. In general, visceral metastases are prioritized over soft tissue or lymph node, and least preferable are bone metastases.

Refer to Section 6.0 for tumor tissue and blood collection time points and Lab Manual for collection and processing details.

10.2 Specimen Banking

Patient samples (tissue and blood) collected for this study will be retained at the University of Michigan. Specimens will be stored indefinitely or until they are used up. If future use is denied or withdrawn by the patient, best efforts will be made to stop any additional studies and to destroy the specimens.

Specimens being stored long-term for potential use not outlined in the protocol are subject to University Policy Governing Tissue Sample Collection, Ownership, Usage, and

11.0 STATISTICAL CONSIDERATIONS

11.1 Study Design/Study Endpoints

This is a multi-center, prospective, one arm, 3 cohort study to evaluate the efficacy of immunotherapy in patients with metastatic cancers and CDK12 loss. Patients with metastatic castration resistant prostate cancer (mCRPC) will be enrolled in Cohort A until 25 evaluable patients are identified. Once Cohort A is full, mCRPC patients will enroll in Cohort C. Patients with other metastatic subtypes will be enrolled in Cohort B.

An Mini-Max Simon Two-Stage design will be used to assess ORR defined as a 50% decline in PSA from baseline in CDK12 loss of function metastatic CRPC patients. It is assumed that an ORR of 30% or more would be interesting for further study compared to a reference ORR of 10% based on the KEYNOTE-199 trial [35]. Accrual of 25 objective PSA response evaluable patients will provide 80% power to detect this difference in ORR with a type I error of 5%. Interim analysis will be completed after 15 objective PSA response evaluable patients (Cohort A only). If 2 or more patients have a PSA response, then the 2nd stage will open and accrue 10 more patients. If 6 or more patients out of 25 have a PSA response, then the treatment will be recommended for further study in this population.

Cohort B will accrue 15 patients with non-prostate histology. A reference ORR of 5% is assumed in patients with non-prostate histology. With 15 patients, we have 76% power to detect an ORR of 25% with a one-sided type I error of 5%. If 3 or more responses are seen in cohort B then we will conclude that there is preliminary evidence of activity.

Cohort C will accrue 25 mCRPC patients. A reference ORR of 10% is assumed, allowing 80% power to detect an ORR of 30% or more with a one-sided type I error of 5%. If 6 or more patients out of 25 have a PSA response, then the treatment will be recommended for further study in this population.

11.2 Sample Size and Accrual

The trial is expected to accrue the total study population of 65 patients harboring CDK12 loss, including 50 objective PSA response evaluable metastatic prostate cancer patients and 15 objective response evaluable patients with non-prostate tumor histology over 2 years.

11.3 Data Analyses Plans

Primary Endpoint Analysis:

The primary endpoint for Cohort A and Cohort C is overall response rate using PSA criteria. The primary analysis will include the response count and proportion with the associated exact 95% binomial confidence interval in the mCRPC cohort. If stage 2 is initiated, then the efficacy analysis methods for the reported response confidence interval will be as described by Koyama and Chen [33].

Secondary Endpoint Analysis:

Efficacy in Cohort B will be described using overall response rate (CR/PR) using RECIST 1.1 criteria. The response count and proportion will be reported with the associated 95% exact binomial confidence interval.

Safety and tolerability of, nivolumab and ipilimumab combination therapy followed by nivolumab monotherapy, or nivolumab monotherapy only, will be described by the frequency and severity of adverse events by CTCAE criteria. The proportion of patients removed from treatment due to AEs will be reported. The number and proportion of patients with dose reductions and/or holds will be reported separately and overall. Each measure will be reported for the entire trial and separately by cohort.

Secondary efficacy time-to-event endpoints including radiographic progression-free survival (rPFS), progression-free survival (PFS), duration of response (DOR) among responders, duration of therapy (DOT), time to progression (TTP) and overall survival (OS) will be reported using Kaplan-Meier methods. The median, if reached, and the 52-week event-free proportion with the associated 95% greenwood formula confidence interval will be reported for each endpoint. For subjects with metastatic CRPC, PSA progression-free survival and time to PSA progression by PCWG3 criteria will also be described for Cohort A using the same the Kaplan-Meier measures described previously. Objective tumor response in patients with measurable disease by RECIST 1.1 criteria will be reported separately by location using PCWG3 recommendations and will include waterfall plots and counts with proportions and the associated 95% confidence intervals. Each endpoint will be reported for all patients if applicable and separately for each cohort.

Quality of Life (QoL) in subjects treated on protocol therapy will be described using EORTC-QLQ-C30 and BPI-SF measures. Baseline will be described using means or medians with an associated variance statistic. Change from baseline will be reported at each time point thereafter with similar descriptive statistics. Each measure will be reported for the overall population and separately by cohort. Each QoL change from baseline will be analyzed using a general linear model with repeated measures for an association with response.

Exploratory Endpoint Analysis

Tumor genome profiling by integrated DNA and RNA sequencing at baseline and optionally at progression will be described using figures representing the profiled patients. These figures will order patients by degree of response (PSA response for Cohort A and Cohort C; and RECIST response for Cohort B). A logistic model with response as the outcome may be used with specific markers as independent covariates to estimate an effect size if a profound pattern is seen. Differences seen in paired samples (baseline and progression) will be described individually and labeled as a responder/non-responder. Immune infiltration in tumor biopsies will be described using figures. Associations of the profiles with the response will be described using counts and proportions.

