This is a multi-center, open label, 3 cohort study of patients with metastatic cancer, either metastatic castration resistant prostate cancer, or metastatic non-prostate cancer whose tumor harbors CDK12 loss of function. Patients with metastatic castration resistant prostate cancer (mCRPC) will be enrolled in cohort A or C, and patients with all other metastatic subtypes will be enrolled in cohort B. Cohorts A and B patients will begin receiving combination therapy with nivolumab 3 mg/kg IV and ipilimumab 1 mg/kg IV every 3 weeks for up to 4 cycles if tolerated, followed by nivolumab maintenance therapy at flat dose 480 mg IV every 4 weeks through the end of the planned study duration, for up to 104 weeks of total therapy. Cohort C patients will receive nivolumab at flat dose 480 mg IV every 4 weeks for up to 104 weeks of total therapy. Cohort C will open after enrollment is complete to Cohort A.

STUDY SYNOPSIS

Title	IMPACT: Immunotherapy in Patients with Metastatic Cancers and CDK12 Mutations
Phase	Phase II
Methodology	Open label, 3 non-randomized cohorts
Study Duration	72 months
Study Center(s)	Multi-site; this is a multicenter trial including the lead site University of Michigan

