2.5 Secondary Endpoints

- 2.5.1 The overall response rate (ORR) in patients with metastatic non-prostate cancer harboring loss of CDK12 function, who are treated with nivolumab and ipilimumab combination therapy followed by nivolumab monotherapy, or nivolumab monotherapy only, as measured by RECIST 1.1 criteria.
- 2.5.2 The frequency and severity of adverse events, as assessed by CTCAE version 4.03 criteria, in patients with metastatic cancer harboring loss of CDK12 function treated with nivolumab and ipilimumab combination therapy followed by nivolumab monotherapy, or nivolumab monotherapy only.,
- 2.5.3 Assess the radiographic progression-free survival (rPFS), progression-free survival (PFS), duration of response (DOR) among responders, duration of therapy (DOT), time to progression (TTP), overall survival (OS) and objective tumor response in patients with measurable disease by RECIST 1.1 criteria. For subjects with metastatic CRPC, determine the PSA progression-free survival and time to PSA progression by PCWG3 criteria.
- 2.5.4 Measure the Quality of Life (QoL) in subjects treated on protocol therapy using EORTC-QLQ-C30 and BPI-SF.

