6.0 STUDY PROCEDURES

6.1 SCHEDULE OF ASSESSMENTS:

	Screening (within 28 days)	C1D1	C2D1	C3D1	C4D1	D1C5+	EOT¹²	Follow Up⁸
Informed Consent	X							
Review Eligibility Criteria	X							
Demographics, Height	X							
Prior and Concomitant Medications	X	X	X	X	X	X	X	
Review Adverse Events¹⁰	X	X	X	X	X	X	X	
Physical Examination, Vital Signs¹, Weight	X	X	X	X	X	X	X	
ECOG Performance Status	X	X	X	X	X	X	X	
Survival Status								X Q3m
Laboratory Assessments								
Pregnancy Test for WOBCP²	X							
CBC with diff, platelets³	X	X	X	X	X	X	X	
Comprehensive Metabolic Panel, including Alk Phos⁴	X	X	X	X	X	X	X	

	Screening (within 28 days)	C1D1	C2D1	C3D1	C4D1	D1C5+	EOT ¹²	Follow Up ⁸
LDH	X	X	X	X	X			
PSA¹¹	X	X	X	X	X	X	X	X
Testosterone¹¹	X				X		X	
TSH, free T3, free T4 (If Clinically Indicated: FSH, LH, ACTH)	X	X	X	X	X	X ⁶	X	
Therapy								
Cohorts A and B Nivolumab 3 mg/kg IV q3 wks for up to 4 doses¹³				X				
Cohorts A and B Ipilimumab 1 mg/kg IV q3 wks for up to 4 doses¹³				X				
Cohorts A and B Nivolumab 480 mg IV q4 wks for up to 23 doses¹³						X		
Cohort C Nivolumab 480 mg IV q4 wks¹⁴				X		X		
Imaging Tumor Assessments								
CT chest	X					X (q 12 wks)		
CT Abdomen/Pelvis or MRI Abdomen/Pelvis⁵	X					X (q 12 wks)		
Tc^{99m} Bone Scan (prostate only)	X					X (q 12 wks)		
QoL: BPI-SF and EORTC QLQ C30	X					X (q 12 wks)		
Correlatives								
Tumor Tissue Archival (CRPC preferred if available)	X							
Tumor Biopsy	X						X ⁷	
Research blood⁹		X	X	X		X (q 12 wks)	X	

1. Vital signs will include temperature, pulse, respirations, blood pressure; height will be obtained at screening only.
2. WOCBP: Women of child bearing potential; urine or serum pregnancy test.
3. CBC with diff includes total WBC, hemoglobin, hematocrit and differential of the WBC including absolute counts.
4. COMP or Comprehensive metabolic profile includes sodium, potassium, chloride, bicarbonate, BUN, creatinine, AST, ALT, alkaline phosphatase, total bilirubin.
5. With or without intravenous contrast, before or on associated visit. CT or MRI (preferred) brain with or without IV contrast if suspected or known brain metastases. Frequency of tumor assessments will be q12 weeks.
6. Every 42 calendar days ± 14 business days. May be delayed if infusion is not scheduled within the window.
7. Optional tissue biopsy collection at progression if subject consents; +/- 14 working days.
8. Follow up with phone call or with clinic visit.

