7.1.1 PSA Response Rate

[figure not shown]
Per PCWG3 criteria, PSA response rate will be defined as the proportion of subjects who have PSA response as defined by at least 50% decline in PSA level from baseline measured twice at least 3 weeks apart. Based on the PCWG3 criteria, a favorable effect on PSA may be delayed for \geq 12 weeks. PSA will be monitored every 4 weeks, but treatment will be planned to continue through early rises for 12 weeks unless other evidence of progression, such as radiographic progression.

Therefore, early rises in PSA before 12 weeks will not be considered when determining PSA response.

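### The QoL repeated-measures model names response as its only term; adding the screening score would tighten the estimate and remove chance baseline imbalance

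*Combined protocol and SAP*

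**What the plan says.** QoL is a secondary endpoint (section 2.5): "Measure the Quality of Life (QoL) in subjects treated on protocol therapy using EORTC-QLQ-C30 and BPI-SF". The schedule of assessments in section 6.1 lists "QoL: BPI-SF and EORTC QLQ C30" at screening and then every 12 weeks in the column for cycle 5 onward.

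Section 11.3 gives the analysis in three steps. At baseline: "Baseline will be described using means or medians with an associated variance statistic". At later visits: "Change from baseline will be reported at each time point thereafter with similar descriptive statistics". Then the only QoL model: "Each QoL change from baseline will be analyzed using a general linear model with repeated measures for an association with response". Summaries are to be given overall and by cohort.

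No other model term is named: not the baseline score, visit or cohort. No covariance structure or rule for missing visits is given, and no power or error rate is attached to QoL.

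Response is an outcome and not an assigned group. The design is "Open label, 3 non-randomized cohorts", and for prostate cancer response means "at least 50% decline in PSA level from baseline measured twice at least 3 weeks apart" (section 7.1.1).

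**The concern.** The screening score is available for the change-score analysis and usually predicts change strongly. A model with response alone leaves that variation in the residual, which widens the interval for the response contrast.

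The groups being compared will also be small. With few responders, their mean baseline score can differ noticeably from that of the non-responders by chance. An unadjusted change score passes part of that imbalance into the estimated association between QoL and response.

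This is the only model-based QoL analysis in the plan, so it is what a reader would cite for a link between response and how patients feel.

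**Working it through.** The plan states no QoL figure to reproduce. It also gives no QoL standard deviation and no correlation, so results are in SD units over an assumed range of ρ.

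**Inputs**
- Patients, from section 11.2: "including 50 objective PSA response evaluable metastatic prostate cancer patients and 15 objective response evaluable patients".
- Responders: 30% of 50 prostate patients is 15 (target rate, section 11.1); 6 of 25 and 3 of 15 are the success thresholds in the same section.
- Assumed: SD 1 at every visit, ρ from 0.3 to 0.7, and equal correlation between all visits.

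**Precision at one visit.** Variance of a change score is 2(1 − ρ). Variance after baseline adjustment is 1 − ρ². Adjusted over unadjusted is (1 + ρ)/2.

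**Precision for the mean of k visits.** Let v = [1 + (k − 1)ρ]/k. Unadjusted variance is v + 1 − 2ρ; adjusted variance is v − ρ². For ρ = 0.5 and k = 4, v = 0.625, so the variances are 0.625 and 0.375, a ratio of 0.60.

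| ρ | Variance ratio, 1 visit | SE reduction | Variance ratio, 4 visits | SE reduction |
|---|---|---|---|---|
| 0.3 | 0.65 | 19% | 0.44 | 34% |
| 0.5 | 0.75 | 13% | 0.60 | 23% |
| 0.7 | 0.85 | 8% | 0.76 | 13% |

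**Chance imbalance.** The SE of the difference in baseline means is √(1/n₁ + 1/n₀). The change-score contrast carries (1 − ρ) times that difference, with opposite sign.

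| Responders v non-responders | SE of baseline difference (SD) | Carried over at ρ = 0.3 / 0.5 / 0.7 (SD) |
|---|---|---|
| 15 v 35 | 0.31 | 0.22 / 0.15 / 0.09 |
| 6 v 19 | 0.47 | 0.33 / 0.23 / 0.14 |
| 3 v 12 | 0.65 | 0.45 / 0.32 / 0.19 |

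This is the same loss as the one-visit precision loss, seen in a single dataset: 2(1 − ρ) = (1 − ρ²) + (1 − ρ)². The two should not be added together.

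**Simulation.** One follow-up visit, 50 patients, 15 responders, no true response effect, 4,000 runs per scenario, two-sided 5% test.

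| Baseline difference | ρ | Change score: mean estimate, rejection | Baseline-adjusted: mean estimate, rejection |
|---|---|---|---|
| None | 0.5 | 0.00, 4.9% | 0.00, 4.5% |
| None | 0.7 | 0.00, 5.5% | 0.00, 5.6% |
| 0.5 SD, both groups regress to a common mean | 0.5 | −0.25, 12.3% | 0.00, 5.1% |
| 0.5 SD, both groups regress to a common mean | 0.7 | −0.15, 9.2% | 0.00, 4.9% |
| 0.5 SD, stable group difference | 0.5 | 0.00, 4.6% | +0.25, 14.3% |
| 0.5 SD, stable group difference | 0.7 | 0.00, 5.4% | +0.15, 10.2% |

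With no baseline difference, the spread of the estimate fell from 0.306 to 0.266 at ρ = 0.5 (13%) and from 0.241 to 0.223 at ρ = 0.7 (7%), in line with the formula. With a 0.5 SD difference in place the gain was smaller: about 10% at ρ = 0.5 and 4% to 5% at ρ = 0.7.

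**The case against.** The strongest objection is that response is not randomised, so choosing between a change score and baseline adjustment is a choice of question, not a correction of an error (Lord's paradox). If responders and non-responders differ at baseline because their disease differs, and that gap persists, the change score is unbiased and adjustment creates the bias. The simulation confirms this, with errors of equal size in opposite directions. This stands, and it limits the point.

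A reader might infer that the planned model will report regression to the mean as an effect of response. The documents do not support that. They give no baseline QoL by response, and the bias is zero if the groups do not differ. If they do differ, its presence depends on stability, which is unknown.

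A second objection is that section 11.3 is silent on covariates and does not exclude them. That is fair: the sentence is under-specified, and omission of baseline is not proven. But a model that names only response is unadjusted as written, and leaving the terms open until response and QoL are known is itself a weakness.

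Third, the stakes are low. At response rates of 10% to 30%, a cohort of 25 has about 2 to 8 responders, so responder numbers dominate the uncertainty under either model. That also stands.

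**Conclusion.** The point holds as a matter of efficiency and specification. For any ρ below 1, and with no systematic baseline difference, an unadjusted change-score model is less precise than one that includes the screening score. The size of the gain rests on the assumed ρ of 0.3 to 0.7, equal variances and, for several visits, equal correlation between visits. It shrinks somewhat if the groups differ at baseline. For imbalance that is purely chance, adjustment is the right correction.

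Bias from a systematic baseline difference is not established in either direction. Neither model supports more than a descriptive association, because response is non-randomised and determined after baseline.

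The improvement is minor but worthwhile. QoL is an unpowered secondary endpoint, and the primary endpoint and the cohort decision rules do not depend on it.

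**What to change.** Replace the model sentence in section 11.3 with a specification along these lines:

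- For each QLQ-C30 and BPI-SF scale, fit a linear mixed model for repeated measures to all available post-baseline visits, with baseline score, visit, response and response-by-visit. State the covariance structure. With baseline in the model, using the score or its change as the outcome gives the same response contrast.
- Include cohort in any pooled analysis, and state which response definition applies. Elsewhere in section 11.3, response is by PSA in Cohorts A and C and by RECIST in Cohort B.
- Report the unadjusted change-score contrast as a sensitivity analysis. If the two disagree, show baseline QoL by response so that the reader can see why.
- Label the result a descriptive association.

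The cost is a few sentences in the plan and no new data, because the screening scores are already scheduled. One limit remains: the schedule shows no QoL at the end-of-treatment visit or in follow-up, so later visits may over-represent responders. Using all available visits does not recover those never scheduled, and the report should say so.
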